#### (3) Vital signs

Vital signs shall present descriptive statistics (number of subjects, mean, standard deviation, median, minimum, maximum) for the quantity of change prior to administration at each visit (DAY 14, DAY 90, DAY 104, DAY 180, DAY 270) compared with the measurement values prior to administration at each visit and the baseline (DAY 0). The difference at each visit compared with the baseline prior to administration shall be analyzed using a paired t-test (Wilcoxon's signed rank test if Shapiro-Wilk test results do not satisfy normality).

The rate of change for the clinically significant abnormalities (Normal / NCS [Not Clinically Significant Abnormal] / CS [Clinically Significant Abnormal]) at each visit (DAY 14, DAY 90, DAY 104, DAY 180, DAY 270) compared with the baseline (DAY 0) prior to administration shall be summarized as frequencies and percentages and

presented as a contingency table. The difference at each visit compared with the baseline prior to administration shall be analyzed using the McNemar-Bowker's test.

In addition, descriptive statistics (number of subjects, mean, standard deviation, median, minimum, maximum) shall be presented for the pre-/post-administration measurement values at each visit and the quantity of change for pre-administration versus post-administration. The differences between pre-administration and post-administration shall be analyzed using a paired t-test (Wilcoxon's signed rank test if Shapiro-Wilk test results do not satisfy normality).

The rate of change for the clinically significant abnormalities (Normal / NCS [Not Clinically Significant Abnormal] / CS [Clinically Significant Abnormal]) of pre-administration versus post-administration shall be summarized as frequencies and percentages and presented as a contingency table. The differences between pre-administration and post-administration shall be analyzed using the McNemar-Bowker's test.

A detailed list shall be presented for clinically significant abnormal results.

#### 4.8 Efficacy Assessment

#### (1) Severity of disease

: The descriptive statistics (number of subjects, mean, standard deviation, median, minimum, maximum) for each item of CMTNS-v2 at the termination visit (DAY 270) compared with the baseline (DAY 0) shall be presented, and the differences at the termination visit compared with the baseline shall be analyzed using a paired t-test (Wilcoxon's signed rank test if Shapiro-Wilk test results do not satisfy the assumption of normal distribution). In addition, descriptive statistics (frequency, percentage) shall be presented for changes in the total score, and a contingency table shall be prepared for the pre-/post-administration differences, and analysis shall be performed using the McNemar-Bowker's test.

In addition, descriptive statistics (number of subjects, mean, standard deviation, median, minimum, maximum) shall be presented for the changes in FDS at each visit (DAY 90, DAY 180, DAY 270) compared with the baseline (DAY 0), and analysis shall be performed using a paired t-test (Wilcoxon's signed rank test if Shapiro-Wilk test results do not satisfy the assumption of normal distribution) for the differences at each visit compared with the baseline.

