The formation of anti-HGF Ab in the blood is checked. Preliminary assessment is made of whether antibody production is correlated between the subject group who are considered to have increased muscle mass and improved function and those who are not. The summary table presents the frequency and ratio of antibody generation in the blood.

However, if no antibody in the blood is produced in any single subject, no results are presented.

For the secondary endpoint, for values before and after treatment, continuous variables present average, standard deviation, median value, minimum value, and maximum value; categorical variables present frequency and percentage. To compare differences of values before and after treatment, continuous variables use a paired t-test or Wilcoxon sign rank test; categorical variables use McNemar's test.

Small group analysis

When conducting the adverse events and efficacy assessments, small group analysis is carried out considering the following items:

- Gender (male, female)
- Age (≤ median, > median)
- Baseline BMI (≤ median, > median)
- Presence or absence of medical history
- Presence or absence of concomitant medications
- Disease severity (CMTNS v2) (mild, moderate)

If the number of subjects that fit into the above subgroups is small in each group, the analysis shall not be conducted on that subgroup. For example, if male subjects are less than 30% of the total subjects, no analysis is performed on gender and whether to analyze shall be determined in a data review meeting prior to datalock.

Retrospect ive biomarker study(To be conducted separately)

PRT NO: VMCMT-001 **Confidential** 2021.06.07 11 / 12

Summary of study schedule

Schedule	Day - 30 to Day - 1	Day -1	Da	ay O	Day 14 ± 5		Day 30 ± 7			Day 104 ± 7		Day 180 ± 7	Day 270 ± 7		
Visit No.	Vieit 1		Visit 2 (Hospitalization)		Visit 3		Outpatient follow-up if	VISIL 4		Visit 5		Visit 6	Visit 7	Early Term	Unsche
Specific Notes	Scree ning	Hospitali zation Day ¹⁵⁾		istration After Administ ration ¹⁶⁾	Admini Befor e	stration After Administ	abnormal test results are present on Day 14 (Second Administrati on)*		istration After Administ ration ¹⁶⁾		urth istration After Administ ration ¹⁶⁾	Outpati ent Follow- up	Outpati ent Follow- up	inati on	duled Visit
Informed consent form	Х														
Subject background survey ¹⁾	Х			5					-						
Medical history survey ²⁾	Х														7(
Physical examination ³⁾	X														

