8.4.4 Secondary Endpoints

(1) Severity of disease

This shall be measured using Charcot-Marie-Tooth Neuropathy Score version 2 (CMTNS-v2) and the functional disability scale (FDS).

: Descriptive statistics (frequency, percentage) for the changes in CMTNS-v2 and FDS at the termination visit (V7) compared with the baseline (V2) shall be presented. A contingency table shall be prepared for the differences before and after administration, and analysis shall be performed using the McNemar's test.

In addition, descriptive statistics (mean, standard deviation, median, minimum, maximum) shall be presented for the changes in FDS at each visit (v4, v6, v7) compared with the baseline (v2), and analysis shall be performed using a paired t-test (wilcoxon signed rank test if the assumption of normal distribution is not satisfied) for the differences at each visit compared with the baseline.

(2) Lower limb function

Changes in lower limb function shall be assessed using the overall neuropathy limitation score (ONLS) and the 10-meter walk test (10MWT).

: Descriptive statistics (mean, standard deviation, median, minimum, maximum) shall be presented for the changes in lower limb function (ONLS leg scale, 10MWT)) at each visit (V4, V6, V7) compared with the baseline (V2), and analysis shall be performed using a paired t-test (Wilcoxon signed rank test if the assumption of normal distribution is not satisfied) for the differences at each visit compared with the baseline.

(3) Degree of Fatty infiltration of lower limb muscles

The muscles of lower limbs shall be imaged with MRI leg scan, and the degree of fatty infiltration of the leg muscles injected with the investigational product shall be measured and evaluated as fat content value (%) at one level for each muscle.

: Descriptive statistics (mean, standard deviation, median, minimum, maximum) shall be presented for the changes in the degree of fatty infiltration of lower limb muscles at the termination visit (V7) compared with the baseline (V2), and analysis shall be performed for the differences before and after administration by using a paired t-test (Wilcoxon signed rank test if the assumption of normal distribution is not satisfied).

(4) Nerve regeneration potential

Nerve conduction studies including compound motor nerve action potential (CMAP), compound sensory nerve action potential (SNAP), and nerve conduction velocity (NCV) shall be performed.

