#### CMTNS-v2

Charcot-Marie-Tooth Neuropathy Score version 2 (CMTNS-v2) is a measurement tool for evaluating the severity of disease. Measurements shall be taken for 9 items which include 3 items for disease symptoms, 4 items for signs, and 2 items for neurophysiological testing. The severity of disease shall be classified according to scores as mild (≤10), moderate (11 to 20), and severe (>20). This clinical study shall target mild to moderate patients. This was performed at Visit 1 (screening), Visit 2 (Day 0), and Visit 7 (termination visit, Day 270) (performed prior to administration at Visit 2 [Day 0]).

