#### 4. Statistical Analysis Method

#### 4.1 General Principles of Statistical Analysis

Since this is a phase 1/2a clinical study and the number of subjects is small, the data from the treatment period and the follow-up period shall be descriptively compared and reviewed. For continuous data, descriptive statistics (number of subjects, mean, standard deviation, median, maximum, minimum) shall be presented, while frequencies and percentages shall be presented for categorical data.

If necessary or if comparisons are possible, statistical test shall be performed. The p-value shall be presented up to 4 decimal places, and a two-tailed test shall be performed under a significance level of 0.05. In addition, for descriptive statistics, numbers with values below the decimal point shall be presented up to 2 decimal places.

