#### (2) Lower limb function

: Descriptive statistics (number of subjects, mean, standard deviation, median, minimum, maximum) shall be presented for the changes in lower limb function (ONLS leg scale, 10MWT)) at each visit (DAY 90, DAY 180, DAY 270) compared with the baseline (DAY 0), and analysis shall be performed using a paired t-test (Wilcoxon's signed rank test if Shapiro-Wilk test results do not satisfy the assumption of normal distribution) for the differences at each visit compared with the baseline.

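### The CMTNS-v2 total score has no planned numeric summary or paired test of its change, unlike every other numeric efficacy variable in the SAP

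*SAP*

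**What the plan says.** SAP 4.8(1) treats CMTNS-v2 in two parts. For the components it plans n, mean, SD, median, minimum and maximum: "each item of CMTNS-v2 at the termination visit (DAY 270) compared with the baseline (DAY 0) shall be presented". These are followed by a paired t-test, or Wilcoxon signed-rank if Shapiro-Wilk rejects normality. For the total it changes method: "descriptive statistics (frequency, percentage) shall be presented for changes in the total score, and a contingency table shall be prepared", tested with McNemar-Bowker.

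The remaining numeric efficacy variables get the numeric treatment. For lower limb function, for example, the numeric statistics "shall be presented for the changes in lower limb function (ONLS leg scale, 10MWT)) at each visit (DAY 90, DAY 180, DAY 270") and a paired test follows. FDS, MRI fat content, and CMAP, SNAP and NCV are handled in the same way.

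Protocol 8.4.4(1) has the same gap. CMTNS-v2 and FDS both get frequencies and a McNemar test ("A contingency table shall be prepared for the differences before and after administration, and analysis shall be performed using the McNemar's test"). Only FDS then gets the numeric analysis as well: "descriptive statistics (mean, standard deviation, median, minimum, maximum) shall be presented for the changes in FDS at each visit (v4, v6, v7").

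Two general rules bear on the point. SAP 4.1 states: "For continuous data, descriptive statistics (number of subjects, mean, standard deviation, median, maximum, minimum) shall be presented". The statistical part of the protocol synopsis states for secondary endpoints: "To compare differences of values before and after treatment, continuous variables use a paired t-test or Wilcoxon sign rank test". Neither mentions the CMTNS-v2 total.

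**The concern.** The total is the score that decides eligibility (above 2 and up to 20) and defines the severity subgroups. It is nevertheless the one numeric efficacy variable whose numeric change has no planned summary or test. The only other efficacy variable left with a McNemar-type test alone is HGF antibody, which is recorded as present or absent.

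The SAP does not say what the categories of the contingency table are. If they are the severity bands, movement within a band is discarded, and at 12 subjects little may be left to analyse. A numeric analysis of the total added after the data are seen would be a post hoc choice.

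**Working it through.** **1. Planned analyses in SAP 4.8**

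| Variable | Numeric summary and paired t/Wilcoxon | McNemar-type test |
|---|---|---|
| CMTNS-v2 items | yes | no |
| CMTNS-v2 total | **no** | yes (Bowker) |
| FDS | yes | no |
| ONLS leg scale, 10MWT | yes | no |
| MRI fat content | yes | no |
| CMAP, SNAP, NCV | yes | no |
| HGF antibody (binary) | not applicable | yes |

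SAP 4.7 is a useful comparison. For laboratory tests and vital signs it plans a paired test of the numeric change and also a three-category table with McNemar-Bowker. The CMTNS-v2 total has the same structure, a number with three bands, but gets only the second analysis.

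**2. Two readings of the table**

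(a) The table lists individual change values. Mean and SD could then be worked out from it. What is missing is the planned numeric summary and the paired test, and the power figures below do not apply.

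(b) The table uses the bands in SAP 3.3: "The severity of disease shall be classified according to scores as mild (≤10), moderate (11 to 20), and severe (>20"). Three bands suit McNemar-Bowker, and a table of raw totals would be unusable with 12 subjects, so this reading is likely. SAP 4.8(1) does not state it. Steps 3 to 5 assume reading (b).

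**3. Band changes needed for p < 0.05**

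The Bowker statistic is the sum over category pairs of (n_ij − n_ji)² / (n_ij + n_ji). If m subjects all move in one direction within one pair, it equals m²/m = m.

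- Chi-square, 1 df, uncorrected (critical value 3.841): m = 3 gives p = 0.083; m = 4 gives p = 0.0455.
- Exact, p = 2 × 0.5^m: m = 5 gives 0.0625; m = 6 gives 0.031.
- Chi-square, 3 df (critical value 7.815): m = 7 gives p = 0.072; m = 8 gives p = 0.046.

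So 4, 6 or 8 of 12 subjects must cross a cut-off in the same direction, depending on a version of the test that the SAP does not specify. If all 12 improved within their bands, the Bowker statistic would be 0, while the exact signed-rank p-value would be 2 × 0.5^12 = 0.0005.

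**4. Size of change to consider**

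The documents give no expected effect or SD for this study, so there is no planned figure to reproduce. Protocol 3.3 reports one CMTNS change, an 8% improvement in a phase 2 study of another drug in CMT1A. It does not state the score version or the reference value. Over eligible totals of 3 to 20 that is 0.08 × 3 = 0.24 to 0.08 × 20 = 1.6 points. Changes of 1 and 2 points are assumed below; 2 points lies above this range.

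**5. Simulation**

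n = 12, two-sided 0.05, 40,000 trials per scenario, integer baseline plus a rounded normal change. Bowker uses df equal to the number of non-empty category pairs, its most favourable version. The three values are for assumed baselines uniform 3–20; normal (mean 12, SD 4) clipped to 3–20; and uniform 8–14.

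| Mean change, SD | Mean number changing band | Bowker power | Paired t power |
|---|---|---|---|
| −1, SD 2 | 1.4, 2.1, 2.9 | 1%, 4%, 11% | 34–35% |
| −2, SD 2 | 1.7, 2.6, 3.7 | 4%, 18%, 37% | 87–88% |
| −2, SD 3 | not listed | 5%, 17%, 27% | 55% |
| +2, SD 2 (worsening) | not listed | 7%, 7%, 29% | 87–88% |

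The SAP's own rule (Shapiro-Wilk, then t or Wilcoxon), in 10,000 trials, gives 34%, 88% and 55% for the three improvement rows.

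Further runs within the 0.24 to 1.6 point range give the same ordering: −1.6, SD 2, about 2–25% against 70%; −1, SD 3, about 1–11% against 18%; −0.5, SD 2, 0.3–5% against 12%.

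**The case against.** The strongest reply is that the general rules already cover the total. CMTNS-v2 is the first secondary endpoint listed, the synopsis gives continuous secondary variables a paired test, and SAP 4.1 requires numeric summaries for continuous data. A general rule need not name each variable. But the specific text handles the total as categorical, and specific text usually governs. SAP 4.1 also makes testing conditional on need or feasibility. An explicit line is still required.

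Second, the item summaries go part of the way. If the total is the sum of its items (the scoring appendix is not among the documents reviewed) and the data are complete, the item mean changes add up to the mean change in the total. That stands. The SD, median, range and paired test of the total do not follow, because they depend on how the items change together within a subject.

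Third, a categorical analysis is a natural fit for an endpoint about severity, and the SAP follows protocol 8.4.4 here. That also stands: the proposal is an improvement to the plan and does not correct a departure from the protocol.

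Fourth, the most striking power figures use a change larger than the one documented anchor, and over most of the anchored range neither test is well powered. This is fair and limits the weight the figures can bear. The numeric test is nevertheless stronger in every scenario examined.

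Finally, the study is single-arm, open-label and safety-primary, the synopsis says it is not intended to assess efficacy, and no decision depends on this p-value. That limits how serious the gap is.

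**Conclusion.** The concern holds. Under either reading, the SAP plans no numeric summary and no paired test for the change in the CMTNS-v2 total, and the general rules do not clearly supply them. Under the likely band reading, the planned test ignores movement within bands. At an assumed 1-point improvement with SD 2 it has 1% to 11% power, against about 35% for the paired test. These figures rest on assumed effects, SDs and baselines and illustrate the loss of information; they do not predict this study's result. The gain is a usable description of change in the severity score, with its precision. It would not be proof of benefit in an uncontrolled study of 12 subjects. The change is worth making because it costs little; the primary safety objective is unaffected.

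**What to change.** In SAP 4.8(1), for the Day 270 minus Day 0 change in the CMTNS-v2 total, add n, mean, SD, median, minimum and maximum, optionally a 95% confidence interval, and the paired t-test or Wilcoxon signed-rank rule already used for the items. Keep the contingency table and the McNemar-type test that protocol 8.4.4 requires, as a supplementary analysis. State that the table's categories are the SAP 3.3 bands, if those are meant, and whether the test is exact or asymptotic.

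The cost is one added analysis sentence and one table row. The total is already collected at Visits 2 and 7, no planned test is removed, and the addition agrees with the synopsis rule. The downside is one more unadjusted p-value in a descriptive study that already tests each item separately.

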#### (2) Lower limb function

: Descriptive statistics (number of subjects, mean, standard deviation, median, minimum, maximum) shall be presented for the changes in lower limb function (ONLS leg scale, 10MWT)) at each visit (DAY 90, DAY 180, DAY 270) compared with the baseline (DAY 0), and analysis shall be performed using a paired t-test (Wilcoxon's signed rank test if Shapiro-Wilk test results do not satisfy the assumption of normal distribution) for the differences at each visit compared with the baseline.

#### (3) Fatty infiltration level of lower limb muscles

: Descriptive statistics (number of subjects, mean, standard deviation, median, minimum, maximum) shall be presented for the changes in the level of fatty infiltration of lower limb muscles at the termination visit (DAY 270) compared with the baseline (DAY 0), and analysis shall be performed using a paired t-test (Wilcoxon's signed rank test if Shapiro-Wilk test results do not satisfy the assumption of normal distribution) for the differences at the termination visit compared with the baseline.

### (4) Nerve regeneration potential

: Descriptive statistics (number of subjects, mean, standard deviation, median, minimum, maximum) shall be presented for the changes in nerve conduction studies (CMAP, SNAP, NCV) at the termination visit (DAY 270) compared with the baseline (DAY 0), and analysis shall be performed using a paired t-test (Wilcoxon's signed rank test if Shapiro-Wilk test results do not satisfy the assumption of normal distribution) for the differences at the termination visit compared with the baseline.

#### (5) HGF antibody generation by VM202

: Descriptive statistics (frequency, percentage) shall be presented for the HGF antibody production at the termination visit (DAY 270) compared with the baseline (DAY 0). A contingency table shall be prepared for the differences at the termination visit compared with the baseline, and analysis shall be performed using the McNemar's test.

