: Descriptive statistics (mean, standard deviation, median, minimum, maximum) shall be presented for the changes in nerve conduction studies (CMAP, SNAP, NCV) at the termination visit (V7) compared with the baseline (V2), and analysis shall be performed for the differences before and after administration by using a paired t-test (Wilcoxon signed rank test if the assumption of normal distribution is not satisfied).

(5) HGF antibody production by Engensis (VM202)

The presence or absence of HGF antibody (anti-HGF Ab) in blood shall be verified with the ELISA method. A preliminary assessment shall be performed on whether antibody production is correlated between the subject group determined to have increased muscle mass and improved function, and the subject group not determined as such.

However, if antibodies in blood were not produced in any of the subjects, the results shall not be presented.

: Descriptive statistics (frequency, percentage) shall be presented for the changes in HGF antibody production at the termination visit (V7) compared with the baseline (V2). A contingency table shall be prepared for the differences before and after administration, and analysis shall be performed using the McNemar's test.

9. Document Management

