#### 1.1.2 Secondary Objectives

To evaluate efficacy following repeated doses of the investigational product (VM202).

- (1) Changes in severity of disease
  - CMTNS-v2 (Charcot-Marie-Tooth Neuropathy Score version 2)
  - FDS (functional disability scale)
- (2) Changes in lower limb function
  - ONLS (overall neuropathy limitation score) leg scale
  - 10MWT (10-meter walk test)
- (3) Changes in fatty infiltration level of lower limb muscles
  - MRI leg
- (4) Nerve regeneration potential
  - CMAP (compound motor nerve action potential)
  - SNAP (compound sensory nerve action potential)
  - NCV (nerve conduction velocity)
- (5) HGF antibody generation by VM202

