#### 1.4 Number of Subjects

#### 1.4.1 Target Number of Subjects and Rationale for Calculation

Using this investigational product, clinical studies have been conducted on six diseases in total since 2007. Although there were no cases in which the drug was applied to CMT1A patients, a total of 18 subjects were recruited in a clinical study on amyotrophic lateral sclerosis among these studies. As a result of assessing safety, it was intended that this clinical study be conducted with 12 subjects considering the addition of indication and the slow progression of disease even though this clinical study also targets similar symptoms.

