#### 4.7 Safety and Tolerability Assessments

#### (1) Adverse events

Summarization and analysis of adverse events shall be performed on treatment-emergent adverse events (TEAEs).

The number of subjects, percentages, 95% confidence interval (Clopper-Pearson Confidence Interval), and number of cases shall be presented for treatment-emergent adverse events (TEAEs), adverse drug reactions (ADRs), adverse events of special interest (AESIs), and serious adverse events/adverse drug reactions (SAEs). In addition, the number of subjects, incidence, and number of cases shall be presented for SAE status of adverse events, SAE reason, severity, causal relationship to the investigational product, relationship to the IP administration procedure, relationship to underlying disease, actions related to the investigational product, corrective treatments, outcomes, etc.

The adverse events, adverse drug reactions, and serious adverse events shall be encoded using the system organ classes (SOCs) and preferred terms (PTs) by using the medical dictionary for regulatory activities (MedDRA, V24.0). The number of subjects with onset, the incidence, the number of cases, etc., shall be presented for the encoded adverse events. In addition, a detailed list shall be presented if serious adverse events occur.

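### McNemar's test on anti-HGF antibody asks whether gains and losses balance; no rate among baseline-negative subjects, and no confidence interval, is planned

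*SAP*

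**What the plan says.** The secondary objective in SAP 1.1.2 is "HGF antibody generation by VM202". Antibody is measured by ELISA before the first dose on Day 0 and again on Day 270; the protocol's visit schedule also has a sample at early termination.

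For the analysis, SAP 4.8(5) asks for frequency and percentage, then a contingency table "for the differences at the termination visit compared with the baseline, and analysis shall be performed using the McNemar's test". Protocol 8.4.4(5) agrees: "A contingency table shall be prepared for the differences before and after administration, and analysis shall be performed using the McNemar's test". Neither says whether the test is exact, continuity-corrected or uncorrected. Neither defines a denominator for the percentage or asks for an interval.

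Adverse events are handled differently. SAP 4.7(1) states: "The number of subjects, percentages, 95% confidence interval (Clopper-Pearson Confidence Interval), and number of cases shall be presented for treatment-emergent adverse events". The SAP also plans Clopper-Pearson intervals for medical history (4.6.2) and for medications and treatments (4.6.3).

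Protocol 8.4.4(5) and SAP 3.3(5) add that antibody results are left out of the report if no subject turns out to have produced antibody.

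**The concern.** Whether the product generates antibody is a question about subjects who start without it: how many of them have it afterwards? McNemar's test asks instead whether the number changing from negative to positive matches the number changing the other way. A baseline-positive subject who turns negative says nothing about whether VM202 induces antibody in others, yet that subject weakens the test result. If every subject starts negative, losses cannot occur, and the p-value is then calibrated against a gain-or-loss coin toss that is not possible in the data.

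The protocol describes the expressed HGF as identical to the body's own protein (3.6) and, for the earlier angina study, reports the absence of anti-HGF antibody among the safety results (3.8). In a study of this size each newly positive subject is informative. What is at stake is a report that gives a p-value where the useful result is a rate with its uncertainty, or that gives nothing when the count is zero.

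**Working it through.** The documents give no power, precision or threshold for this endpoint, so there is no figure of the plan's own to reproduce.

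**Inputs from the documents.** Sample size: "it was intended that this clinical study be conducted with 12 subjects" (SAP 1.4.1). Error level: "a two-tailed test shall be performed under a significance level of 0.05" (SAP 4.1).

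**Assumptions.** All 12 subjects have both samples. Baseline antibody status is not given, so no losses is the main case and one loss is the alternative.

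**Formulas.** With b gains and c losses:
- Exact: p = 2 × P(X ≥ b), X ~ Binomial(b + c, 0.5). With c = 0 this is 2 × 0.5^b.
- Continuity-corrected: (|b − c| − 1)² / (b + c) on chi-square with 1 df.
- Uncorrected: (b − c)² / (b + c) on chi-square with 1 df.
- Clopper-Pearson 95% limits for b/12 from beta quantiles.

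**Step 1: no losses.**

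| Gains of 12 | Exact p | Corrected p | Uncorrected p | Rate (Clopper-Pearson 95%) |
|---|---|---|---|---|
| 3 | 0.250 | 0.248 | 0.083 | 25% (5.5 to 57.2%) |
| 4 | 0.125 | 0.134 | 0.0455 | 33.3% (9.9 to 65.1%) |
| 5 | 0.0625 | 0.074 | 0.025 | 41.7% (15.2 to 72.3%) |
| 6 | 0.031 | 0.041 | 0.014 | 50% (21.1 to 78.9%) |

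The largest non-significant count is 5 with the exact or corrected test and 3 with the uncorrected test. At 4 or 5 conversions the conclusion depends on a choice that the documents leave open.

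**Step 2: one loss.**

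| Gains | Exact p | Corrected p | Uncorrected p |
|---|---|---|---|
| 6 | 0.125 | 0.131 | 0.059 |
| 7 | 0.070 | 0.077 | 0.034 |
| 8 | 0.039 | 0.0455 | 0.020 |

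For six gains the exact calculation is 2 × (7 + 1)/2⁷ = 0.125, against 2/2⁶ = 0.031 without the loss. The largest non-significant count rises to 7 (exact or corrected) or 6 (uncorrected). The number of converters has not changed; only their denominator has, to at most 12 − 1 = 11 baseline-negative subjects.

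**Step 3: no gains.** For 0/12 the upper Clopper-Pearson limit is 1 − 0.025^(1/12) = 26.5%. This is the case in which the plan presents nothing.

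Fewer tested subjects would change the percentages but not the count thresholds for a given number of losses.

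**The case against.** McNemar's test is the standard test for paired binary data, and equal gains and losses is its ordinary null. Both documents say that the data are to be reviewed descriptively because the study is small, with tests where needed or possible, so low power is common to nearly every test here. This is fair. The objection to the test is therefore not its power but that it answers a different question from the objective, whatever the sample size.

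Several stronger readings are tempting, and the documents do not support them:

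- *Seroconverters are hidden.* They are not. The negative-to-positive cell of the contingency table is their count, baseline-positive subjects have their own row, and the protocol synopsis also asks for the frequency and ratio of antibody generation.
- *The McNemar p-value is the only antibody analysis.* Protocol 8.4.4(5) and SAP 3.3(5) include a preliminary look at antibody against muscle mass and function, and SAP 4.9 allows subgroup comparisons of the efficacy assessments, which include antibody.
- *A non-significant result will be declared to mean no antibody generation.* No rule in either document says so. That is a risk of misreading, not a planned conclusion.
- *Antibody is a safety endpoint analysed wrongly.* Both documents list it with efficacy. The safety relevance is a reasonable inference from protocol 3.6 and 3.8, but it is an inference.
- *The test throws away information that counting would keep.* At a true rate of 25% with no losses, the test is significant with probability 5.4% (exact) or 35.1% (uncorrected), while at least one converter is seen with probability 97%. These are not comparable: seeing one converter is not a test, and the plan shows the count in any case.

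**Conclusion.** The point holds as a mismatch between question and analysis, with a cheap remedy, on a secondary endpoint. The planned test cannot estimate or bound the rate of new antibody, and a single loss moves six conversions from exact p=0.031 to 0.125. A reader might infer that up to 5 of 12 conversions (42%) will always come out non-significant. That holds only with no losses and the exact or continuity-corrected version; with the uncorrected chi-square the limit is 3 of 12 (25%). The thresholds rest on the assumed number of losses, and the offset matters only if some subject is positive at baseline, which the documents neither report nor exclude.

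What is missing under any version of the test is a rate with baseline-negative subjects as its denominator, its confidence interval, and a result when the count is zero. The last gap is practical: the protocol reports no anti-HGF antibody in the earlier angina study, so zero is a plausible outcome here.

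**What to change.** In SAP 4.8(5), with matching wording in protocol 8.4.4(5) or a note in the SAP that it departs from the protocol:

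1. Make the main antibody result the number and percentage of subjects negative on Day 0 who are positive at Day 270, or at early termination, with a Clopper-Pearson 95% confidence interval.
2. List each seroconverter, and show baseline-positive subjects separately with their later status.
3. Drop McNemar's test for this endpoint. If it is kept, name the version and state that no conclusion on antibody generation will be drawn from it.
4. Delete the rule, also in SAP 3.3(5) and the protocol synopsis, that withholds antibody results when no subject produces antibody. Report 0/n with its upper limit.

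The cost is one small table and a few words of text. The interval method is already specified in the SAP for adverse events, and no new samples are needed.
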